3.7.5 Secondary and Exploratory Endpoint Analyses

All the secondary and exploratory endpoints will be summarized and analyzed based on the mITT Population. In addition to the overall analysis, analyses by exposure group, [REDACTED] group, and final study drug dose will also be performed. No adjustments will be made for multiplicity.

For continuous variables, the ANCOVA model specified for the primary analysis will be used. For patients with missing values at Week 12, the LOCF method will be used for imputation. Normality will be tested for the model residuals.

For Lp(a), statin subgroup and baseline Lp(a) subgroup (≤ 10 or > 10 nmol/L) will be summarized and analyzed, as well as other cut-offs (70 nmol/L) and quartile analyses as appropriate. The statin subgroup will also be explored for ApoB, ApoCIII, and other lipids if appropriate. Other subgroup analysis will also be conducted as needed.

For triglycerides and [REDACTED], a logarithm transformation may be performed prior to fitting the ANCOVA model for change in triglycerides and [REDACTED]. The treatment comparisons will be transformed back to the difference in percent change from baseline. If the model residuals for the ANCOVA model of the logarithm transformed data still do not satisfy the normality assumption, the Wilcoxon rank-sum test will be performed as the main analysis to compare the percent change from baseline to Week 12. In addition to the Wilcoxon rank-sum test, the Hodges-Lehmann method will be used to estimate the median difference and its corresponding 95% confidence interval.

For certain efficacy endpoints, the MMRM method may be used to test the robustness of the results with treatment and visit as factors, and treatment by visit interaction. The treatment difference at Week 12 will be estimated from the MMRM.

For categorical variables, Fisher's exact test will be used to compare the percentages between MGL-3196 doses versus placebo at each post-baseline visit.

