2.1.2 Secondary Objectives

The secondary objectives of this study are the following:

- To evaluate the safety profile, including any changes in thyroid axis hormones, and tolerability of once-daily oral dosing regimen of MGL-3196 versus placebo after 12 weeks in patients with HeFH;
- To determine the effect of once-daily oral dosing regimen of MGL-3196 versus placebo for 12 weeks on the percent change from baseline on the following assessments in patients with HeFH:
 - Non-high-density lipoprotein cholesterol (non-HDL-C),
 - Apolipoprotein B (ApoB),
 - Total cholesterol (TC)/high-density lipoprotein cholesterol (HDL-C) ratio,
 - Triglycerides,
 - Lipoprotein(a),
 - ApoB/Apolipoprotein A1 (ApoA1) ratio, and
 - Lipoprotein particle assessment;
- To determine the effect of once-daily oral dose of MGL-3196 versus placebo for 12 weeks on the absolute change from baseline in LDL-C in patients with HeFH;
- To determine the effect of all patients (100 and 60 mg groups) on percent change from baseline in LDL-C; and
- To determine the effect of exposure to MGL-3196 on LDL-C lowering.

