2.3 Study Endpoints

2.3.1 Efficacy Variables

The primary efficacy parameter is mean percent change from baseline in LDL-C.

The secondary efficacy parameters include the following:

- Mean percent change from baseline in non-HDL-C, ApoB, TC/HDL-C ratio, triglycerides, lipoprotein(a) (Lp(a)), ApoB/ApoA1 ratio, Apolipoprotein CIII (ApoCIII), and lipoprotein particle assessment;
- Absolute change from baseline in LDL-C;
- Mean percent change from baseline in LDL-C for all patients on study drug (60-100 mg); and
- Mean percent change from baseline in LDL-C according to MGL-3196 exposure.

The exploratory efficacy parameters include the following:

- [REDACTED]
- [REDACTED]
- [REDACTED]
- [REDACTED]

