3.7.2 Primary Efficacy Analyses of LDL-C

The primary efficacy variable will be the percent change in LDL-C from baseline to Week 12. Summary statistics (number of patients, mean, standard deviation, median, minimum, and maximum) at all visits and change and percent change from baseline will be provided.

The primary efficacy variable, the percent change in LDL-C from baseline to Week 12, will be analyzed using an analysis of variance (ANOVA) model with treatment (MGL-3196 or placebo) as a factor based on the mITT population. For any patients in the mITT Population with a missing primary efficacy variable, the last post-baseline observation carried forward (LOCF) method will be used. The least-squares mean, 95% confidence interval, and p-value will be provided for the comparison of MGL-3196 versus placebo.

Sample SAS® code is provided below:

```
*****

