** PCHG = Percent change in LDL-C from Baseline to Week 12      **
** TRT = Treatment group where 0 = placebo, 1= MGL-3196           **
*****
PROC GLM;
  CLASS TRT;
  MODEL PCHG = TRT;
  LSMEANS TRT / e pdiff=control("0") cl;
RUN;
```

In addition to the percent change from baseline to Week 12 in LDL-C, the change in LDL-C from baseline to Week 12 will be analyzed using an analysis of covariance (ANCOVA) model with treatment as a factor and the baseline value as a covariate. For any patients in the mITT Population with a missing primary efficacy variable, the LOCF method will also be used.

Sample SAS® code is provided below:

```
*****

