** CHG = Change in LDL-C from Baseline to Week 12      **
** TRT = Treatment group where 0 = placebo, 1= MGL-3196           **
** BASE = Baseline LDL-C                                     **
*****
PROC GLM;
```

```
CLASS TRT;  
MODEL CHG = TRT BASE;  
LSMEANS TRT / e pdiff=control("0") cl;  
RUN;
```

The same analysis models for Week 12 LDL-C are also used to analyse the percent change and change in LDL-C from baseline at Week 2 and Week 4 LOCF.

The primary efficacy analysis will be performed based on the Per Protocol Population to evaluate the robustness of the primary efficacy analysis.

Other imputation method for missing values of Week 12 LDL-C will be evaluated, including multiple imputation and Mixed Model for Repeated Measurements (MMRM) method based on the mITT population. The multiple imputation method will use statin group (80 mg Atorvastatin, 20/40 mg Rosuvastatin, or No/Low Dose Statin), baseline and all the post-baseline valid LDL-C values as references for the imputation with the monotone missingness assumption. The MMRM method will include treatment and visit as factors, and treatment by visit interaction.

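### SAP 3.7.5 sends percent-change secondary endpoints to an ANCOVA whose only written response is absolute change, and gives Lp(a) no log or rank route

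*SAP*

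**What the plan says.** **Endpoints.** SAP 2.1.2 sets the lipid objective as MGL-3196 "versus placebo for 12 weeks on the percent change from baseline on the following assessments". SAP 2.3.1 lists mean percent change for non-HDL-C, ApoB, TC/HDL-C, triglycerides, Lp(a), ApoB/ApoA1, ApoCIII and the particle assessment. Absolute change is listed only for LDL-C.

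**Models in SAP 3.7.2.** Percent change in LDL-C "will be analyzed using an analysis of variance (ANOVA) model with treatment (MGL-3196 or placebo) as a factor", with no baseline term. Separately, "the change in LDL-C from baseline to Week 12 will be analyzed using an analysis of covariance (ANCOVA) model", and the code is "MODEL CHG = TRT BASE", with CHG defined as change. No other ANCOVA appears in that section.

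**Rule for secondary endpoints.** SAP 3.7.5 states: "For continuous variables, the ANCOVA model specified for the primary analysis will be used". For triglycerides and one redacted variable it allows a log transformation and adds: "The treatment comparisons will be transformed back to the difference in percent change from baseline". If residuals on the log scale are still non-normal, those two variables go to a Wilcoxon test on percent change with a Hodges-Lehmann estimate. For Lp(a) it plans subgroups at 10 and 70 nmol/L and quartiles, but no transformation or rank test. Multiplicity is not adjusted.

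**Protocol.** Section 10.2.1.1 makes the primary analysis an ANCOVA with treatment and baseline. Section 10.2.1.2 applies that same model to the continuous secondary endpoints and permits a log transformation for some variables without naming them.

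**The concern.** The cross-reference in SAP 3.7.5 points to something the SAP does not contain. It fits the protocol, where the primary analysis was an ANCOVA. The SAP changed the primary test to an ANOVA, and the only ANCOVA left in 3.7.2 is the absolute-change one. A programmer who follows the text would produce p-values and confidence intervals for absolute change, while the endpoint is percent change. A programmer who reads it the other way would produce a different analysis of the same endpoint. Nothing in the SAP settles which, so the choice could be made after results are seen.

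For a marker with a narrow baseline range the two scales nearly agree. Lp(a) may have a wide range. On the raw scale the few patients with the highest values then dominate both the estimate and its standard error, and a real proportional fall can be missed. SAP 3.7.5 has residual normality tested, but says what follows from a failed test only for triglycerides and the redacted variable.

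**Working it through.** **1. Endpoint against test, from the text alone.**

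| Secondary endpoint | Response in SAP 2.3.1 | Test the SAP names |
|---|---|---|
| LDL-C, all treated patients | percent change | ANOVA on percent change (3.7.2): matches |
| LDL-C by exposure | percent change | ANOVA and ANCOVA (3.7.3): matches |
| LDL-C, absolute | change | ANCOVA on change (3.7.2): matches |
| Triglycerides | percent change | optional log route or Wilcoxon, returned as percent change (3.7.5): conditional match |
| Non-HDL-C, ApoB, TC/HDL-C, Lp(a), ApoB/ApoA1, ApoCIII, particles | percent change | ANCOVA whose only written response is change: mismatch or ambiguous |

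**2. The plan's own figure.** SAP section 4 gives 27 completers per group for 90% power (difference 20, SD 20, alpha 0.025). The noncentrality is 20 / (20 × √(2/27)) = 3.67 on 52 df. Two-sided exact power is 91.0% at 27 and 89.8% at 26, so the figure reproduces. It concerns percent change in LDL-C. No power is stated for any other endpoint.

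**3. Lp(a) under assumed inputs.** From the documents: 70 vs 35 patients. Assumed: median 40 nmol/L, lognormal baseline, true fall 25%, within-person CV 25% at each visit, two-sided 0.05.

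Hand check for the log ratio: SD = √(2 × ln(1 + 0.25²)) = 0.348; SE = 0.348 × √(1/70 + 1/35) = 0.0721; effect = ln 0.75 = −0.288; ratio 3.99, which gives power of about 98%.

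Simulation (6,000 trials per row; values floored at 1 nmol/L), power in %:

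| Log-SD | Additive noise | Absolute-change ANCOVA | Percent-change ANCOVA | Log-ratio ANCOVA | Loss, absolute vs log |
|---|---|---|---|---|---|
| 0.6 | none | 93 | 98 | 98 | 5 |
| 0.8 | none | 87 | 98 | 98 | 11 |
| 1.1 | none | 72 | 97 | 98 | 26 |
| 1.4 | none | 57 | 97 | 98 | 41 |
| 0.6 | 3 nmol/L | 92 | 90 | 95 | 2 |
| 0.8 | 3 nmol/L | 85 | 80 | 91 | 6 |
| 1.1 | 3 nmol/L | 72 | 65 | 83 | 11 |

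A separate run gave losses of 4, 11, 27 and 41 without noise and 2, 5 and 14 with it, so the losses are good to about 3 points. With this noise, percent-change ANCOVA does no better than absolute change.

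**4. A second error model.** Here the error sits in the response (SD of percent change 30% to 40%, true fall 20% to 30%). With 3 nmol/L noise and log-SD 1.0 to 1.3, percent-change ANCOVA leads absolute change by 4 to 14 points and log-ratio ANCOVA by 11 to 22. Only the log-ratio advantage holds under both models.

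**5. Narrow-range marker.** For an ApoB-like marker (log-SD 0.25, CV 10%, fall 8%), power is 83% for absolute change and 85% for percent change or log ratio: about 2 points.

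**6. Type I error.** With no effect, every model rejected in about 4% to 5% of trials.

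**The case against.** The strongest reply is that the word model in SAP 3.7.5 may mean only treatment plus baseline, applied to each endpoint as SAP 2.3.1 defines it. Protocol 10.2.1.2 uses the term that way, and the triglyceride result is returned as a percent change. This reading is possible and stands as an alternative. It does not remove the problem, because the SAP would then allow two responses for one endpoint. The descriptive plan in SAP 3.7.1 does not settle it either, since it offers change or percent change.

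A reader might infer that the percent-change secondary endpoints have no planned test at all. The documents do not support that: the LDL-C endpoints have matching tests, and triglycerides and the redacted variable have a conditional route.

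A reader might also infer that Lp(a) certainly loses much of its power. The documents do not support that either. They give no Lp(a) median, SD, within-person variation or planning effect. The cut-offs at 10 and 70 nmol/L suggest spread but do not fix a log-SD. The Phase 1 remark about measurable Lp(a) in Protocol 1.1.1 comes from healthy-volunteer studies. At log-SD 0.6 the loss is small.

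Two further points stand. These endpoints are nominal, with no multiplicity control. The planned Lp(a) subgroup and quartile analyses go some way against domination by high values, although they do not supply the overall test.

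**Conclusion.** The point holds as a mismatch between endpoint and test. SAP 3.7.5 refers to a primary-analysis ANCOVA that the SAP does not have, and the only ANCOVA in SAP 3.7.2 has absolute change as its response. Seven types of percent-change endpoint are therefore either tested on another quantity or left without a named response. This rests on the text alone.

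The effect on Lp(a) is conditional. Under the inputs assumed above, the loss against a log-ratio ANCOVA is about 4, 11, 27 and 41 points at log-SD 0.6, 0.8, 1.1 and 1.4. With 3 nmol/L additive noise it is about 2, 5 to 6 and 11 to 14 points at 0.6, 0.8 and 1.1. That Lp(a) has no log or rank route assumes it is not the redacted variable; it is named openly in the preceding paragraph of SAP 3.7.5, but the redaction cannot be read. For ApoB-like markers the issue is what is estimated, not power. False-positive risk is unchanged. It should be corrected, but it does not touch the primary test.

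**What to change.** In SAP 3.7.5, replace the cross-reference with: for each secondary endpoint in 2.3.1 defined as percent change, fit `PCHG = TRT BASE`; absolute change is supportive. This restores the protocol's treatment-plus-baseline form. It differs from the SAP's primary ANOVA by the baseline term, which the SAP should state.

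For Lp(a), pre-specify the route already written for triglycerides: fit `log(Week 12/baseline) = TRT log(BASE)`, and back-transform to a relative percent difference with a 95% CI. Use Wilcoxon and Hodges-Lehmann on percent change as the fallback. Set values below the assay limit to that limit at both visits.

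Cost: a few sentences and one or two model lines, with no new data. Downside: the Lp(a) result becomes a ratio of geometric means, which is not the mean percent change of SAP 2.3.1, so the arithmetic mean percent change should be reported beside it.

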3.8 Analysis of Safety

The safety endpoints for this study include: AEs, safety laboratory assessments, vital signs, 12-lead ECGs, physical examinations, and clinical assessments. The safety endpoints will be summarized based on the Safety Population.

3.8.1 Adverse Events

Treatment-Emergent Adverse Events (TEAEs) are defined as adverse events that are new or worsen after the first dose of study drug. AE worsening applies to severity or relationship to study drug.

A summary overview of TEAEs will be provided, which presents the number and percentage of patients in each treatment group from the Safety Population satisfying each of the following categories:

- Any TEAEs,
- Maximum severity of TEAEs,
- Study drug-related TEAEs,
- Maximum severity of study drug-related TEAEs,
- All treatment-emergent serious adverse events (SAEs),
- All study drug-related TE-SAEs,
- TEAEs leading to death,
- TEAEs leading to study drug discontinuation, and
- Study drug-related TEAEs leading to study drug discontinuation.

Adverse events will be coded using MedDRA. The number and percentage of patients with TEAEs will be summarized by their MedDRA preferred term within system organ class and by treatment. AEs will be counted by the number of events as well as the number of patients. For event count summaries, multiple AE events with the same MedDRA coded terms (preferred term and system organ class) and onset date and time from the same patient will only be counted once. For patient count summaries, multiple AE events with the same MedDRA coded terms (preferred term and system organ class) from the same patient will only be counted once.

The number and percentage of patients with TEAEs will be summarized by reported maximum severity within each MedDRA preferred term within system organ class and by treatment.

The number and percentage of patients with TE-SAEs, any drug-related TEAEs, drug-related TE-SAEs, and TEAEs and TE-SAEs that lead to study drug discontinuation will be summarized by preferred term within system organ class and by treatment. In these summaries, any patients reporting multiple episodes of the same TEAE (i.e., same preferred term and system organ class) will be counted once.

All SAEs will be listed with an indication of whether the SAE was treatment emergent or started prior to treatment.

All TEAEs that are reported as leading to study drug discontinuation will be listed.

3.8.2 Clinical Laboratory Assessments

3.8.2.1 Chemistry and Hematology

Descriptive statistics of each chemistry and hematology parameter will be presented for baseline values and for values and changes from baseline at each post-baseline visit. These will be presented by treatment group for each parameter using the Safety Population.

Counts and percentages of patients with any post-baseline observation that is below the lower limit of normal (<LLN) or above the upper limit of normal (>ULN) will be summarized for each chemistry and hematology parameter by treatment group and overall.

The liver enzyme parameters (ALT, AST, creatine kinase [CK], and GGT) will be analyzed for the overall Safety Population by active and placebo groups, and by exposure group, final dose group, and SHBG group. Statin subgroup will also be explored. Patients with mild liver diseases will not be included in the analysis of liver enzyme parameters, since the liver enzyme value will be affected. The possible liver disease may include, but is not limited to: elevated

liver enzymes (elevated direct bilirubin ≥ 0.3 mg/dL, or GGT > 100 U/L) or large amount of alcohol use.

The shift from baseline value to the worst post-baseline value will be summarized for selected parameters (AST, ALT, total bilirubin, alkaline phosphatase, creatinine, and CK). Shift categories will be based on normal ranges (<LLN, Normal, >ULN).

3.8.3 12-Lead Electrocardiogram

ECG parameters (heart rate, PR interval, QRS interval, QT interval, QTcB interval, QTcF interval, RR Interval, and overall interpretation) will be summarized by treatment group using descriptive statistics for the Safety Population. The average of 3 readings will be used in the summaries. For the overall interpretation, the most severe interpretation at the visit will be summarized. The count and percentage of patients with QTcF and/or QTcB above thresholds (>450 msec, >480 msec, >500 msec) or change from baseline above thresholds (>30 msec, >60 msec) will be summarized by treatment group for the Safety Population.

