4.2 Exclusion Criteria

Patients who meet any of the following criteria will be excluded from participation in the study:

1. Homozygous familial hypercholesterolemia;
2. Low-density lipoprotein (LDL) or plasma apheresis within 2 months prior to randomization;
3. New York Heart Association class III or IV heart failure, or known left ventricular ejection fraction $<30\%$;
4. Uncontrolled cardiac arrhythmia, including confirmed QT interval corrected using Fridericia's formula (QTcF) >450 msec for males and >470 msec for females at the screening electrocardiogram (ECG) assessment;

5. Myocardial infarction, unstable angina, percutaneous coronary intervention, coronary artery bypass graft, or stroke within 3 months prior to randomization;
6. Type 1 diabetes, or newly diagnosed or uncontrolled type 2 diabetes (hemoglobin A1c [HbA1c] >8%);

7. History of significant alcohol consumption for a period of more than 3 consecutive months within 1 year prior to screening;

Note: Significant alcohol consumption is defined as average of >20 g/day in female patients and >30 g/day in male patients;

8. Hyperthyroidism;
9. Thyroid replacement therapy
10. Hypothyroidism;

Note: If TSH is up to 1.5 x ULN on screening with normal free T4, one repeat test is allowed to confirm the elevation in TSH. If TSH and free T4 are normal upon repeat testing, patient may be included. Patients with a history of thyroid hormone replacement therapy or patients who have discontinued thyroid hormone replacement therapy (including thyroxine) ≥ 2 months prior to randomization may be included in the study if this criterion is met;

11. Evidence of chronic liver disease;
12. Hepatitis B, as defined by the presence of hepatitis B surface antigen (HBsAg);
13. Hepatitis C, as defined by the presence of hepatitis C virus (HCV) antibody (anti-HCV) and HCV ribonucleic acid (RNA). Patients with positive anti-HCV who test negative for HCV RNA at screening will be allowed to participate in the study;
14. Serum ALT $>1.5 \times$ ULN (one repeat allowed);
15. Estimated glomerular filtration rate <60 mL/min;
16. Creatine kinase $>3 \times$ ULN (one repeat allowed);
17. History of biliary diversion;
18. Positive for human immunodeficiency virus (HIV) infection;
19. History of malignant hypertension;
20. Systolic blood pressure >160 mmHg or diastolic blood pressure >100 mmHg at screening or randomization and confirmed at an unscheduled visit;

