3.2.2 Per Protocol Population

The Per Protocol Population will include all mITT patients who finish the Week 12 visit with valid LDL-C measurements, have sufficient treatment compliance, and do not have any major protocol deviations. The following will be evaluated for major deviations prior to unblinding of the treatment allocation:

- Patients who violated eligibility criteria;
- Patients who did not complete the study;
- Patients who were <80% compliant with study drug;
- Patients who took prohibited concomitant medications;
- Patients who were unblinded; and
- Patients who had other substantial protocol deviations that may impact the efficacy assessment.

The Per Protocol Population will be used to assess robustness of the primary efficacy analysis results.

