3.2.3 Safety Population

The Safety Population will include all patients who are randomized in the study and receive at least 1 dose of study drug and will be used for all safety analyses.

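### SAP 3.8.2.1 drops patients with liver abnormalities from the liver enzyme analysis by an open, undated rule, so an on-drug rise in GGT or direct bilirubin can remove a patient

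*SAP*

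**What the plan says.** SAP 3.8.2.1 says of four analytes (GGT, ALT, AST and CK) that they "will be analyzed for the overall Safety Population by active and placebo groups, and by exposure group, final dose group, and SHBG group". It adds that statin subgroup will be explored, and then restricts the set: "Patients with mild liver diseases will not be included in the analysis of liver enzyme parameters, since the liver enzyme value will be affected". The qualifying conditions open with "The possible liver disease may include, but is not limited to" and continue with raised liver tests ("elevated direct bilirubin ≥ 0.3 mg/dL, or GGT > 100 U/L") or heavy alcohol use, for which no amount is given. No visit is attached to either laboratory limit.

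The general rules differ. SAP 3.2.3 puts in the Safety Population all randomized patients who "receive at least 1 dose of study drug and will be used for all safety analyses", and Protocol 10.1 defines it the same way. SAP 3.8 adds: "The safety endpoints will be summarized based on the Safety Population". Protocol 10.2.2, on the analysis of safety, contains no liver exclusion.

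**The concern.** A safety analysis should not select patients on a value that the drug may change. Protocol 1.1.2 treats liver enzymes as a class concern. It reports that an earlier thyroid agonist raised AST, ALT, bilirubin and GGT in HeFH patients, visibly by week 2. If MGL-3196 did the same, an undated GGT or direct bilirubin trigger would remove affected patients, more of them from the active arm, and would pull the comparison towards no effect.

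The open list adds a second problem. Two analysts could build different datasets from this paragraph, and either could do so after seeing treatment codes. The analysis at stake is the one meant to show whether enzyme changes follow exposure, final dose or SHBG response.

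**Working it through.** The plan gives no figure on this point to reproduce, so the check is mainly of the text, followed by the weight of one patient.

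**1. Population.** SAP 3.8.2.1 names the overall Safety Population and then removes part of it. SAP 3.2.3, SAP 3.8 and Protocol 10.1 allow no such removal.

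**2. Timing.** Protocol 9.8 lists GGT and direct bilirubin in the chemistry panel at Screening, Day 1 and Weeks 2, 4, 8, 12 and 16. Weeks 2 to 12 are on treatment. The SAP states timing for other groupings: section 3.7.3 specifies baseline BMI, TSH averaged over screening and baseline, and SHBG change from baseline to Week 12. Here it states none, so an on-drug value can qualify. GGT is then both an analysed outcome and a trigger.

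**3. Closure.** The list is open and the alcohol item has no threshold, although Protocol 4.2 has one: "Significant alcohol consumption is defined as average of >20 g/day in female patients and >30 g/day in male patients".

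**4. Lock.** For the Per Protocol set, SAP 3.2.2 says: "The following will be evaluated for major deviations prior to unblinding of the treatment allocation". Section 3.8.2.1 has no counterpart.

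**5. Entry criteria.** Protocol 4.2 already excludes chronic liver disease, ALT above 1.5 x ULN and significant alcohol use. Part of what a pre-dose exclusion would remove is therefore absent from the start. GGT and direct bilirubin are not entry criteria.

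**6. Weight of one patient.** SAP 4 gives 70 on MGL-3196 and 35 on placebo.
- 1/70 = 1.4 percentage points; 1/35 = 2.9 points.
- Protocol 1.2.2 expects about 25-30% of patients above target exposure. Assume these become the 60 mg group: 0.25 x 70 = 17.5 (taken as 18) to 0.30 x 70 = 21. Then 1/21 = 4.8 and 1/18 = 5.6 points.
- The 100 mg group would hold 70 - 21 = 49 to 70 - 18 = 52, so one patient is 1/52 = 1.9 to 1/49 = 2.0 points.

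**7. Illustration on a rate.** Suppose 2 patients in the 60 mg group have an elevation and one is excluded for an on-drug trigger. Then 2/18 = 11.1% becomes 1/17 = 5.9%, or 2/21 = 9.5% becomes 1/20 = 5.0%. The count of 2 is assumed. So is the use of a rate, since the SAP does not say how these data will be analysed.

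**8. Illustration on a mean.** This simulation rests wholly on assumptions: log-normal GGT, baseline median 25 U/L, between-patient log-SD 0.6 to 0.8, within-patient log-SD 0.35 and one post-baseline value. Ranges run over the two log-SDs.

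| True rise on drug | Dropped if on-drug GGT >100 counts: drug / placebo | Drug-placebo difference in mean GGT change (U/L): no exclusion | On-drug rule | Pre-dose rule |
|---|---|---|---|---|
| 1.2-fold | 4-8% / 2-6% | 6.4-7.3 | 5.2 | 6.1-6.3 |
| 1.5-fold | 8-13% / 2-6% | 15.9-18.4 | 11.7-12.2 | 15.4-15.8 |
| 2-fold | 16-21% / 2-6% | 31.9-36.7 | 20.4-21.6 | 30.8-31.5 |

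Only the direction carries over to the trial: an on-drug rule removes more drug than placebo patients and shrinks the difference. A pre-dose rule selects both arms alike, and its smaller change reflects a population without high baselines.

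**The case against.** The strongest reply is that the sentence was meant for pre-existing disease. Its stated reason, that the condition affects the enzyme value, is the language of a confounder. On that reading the defect is little more than a missing reference to baseline. The reading is plausible and would largely remove the bias. The SAP does not state it, though, and it leaves the open list, the missing lock and the conflict over the population.

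Second, a signal would still be reported. The by-visit values and changes are explicitly on the Safety Population (SAP 3.8.2.1, with the statistics in SAP 3.1). The counts outside the normal range and the shift table carry no stated exclusion. Adverse events use the full Safety Population, SAP 3.9 plans an unrestricted look at concentration against safety, and SAP 5 promises listings of all data. This stands, and it limits the consequence. But the shift table omits GGT and direct bilirubin, SAP 3.9 does not name liver enzymes, and none of these outputs is specified for liver enzymes by exposure, final dose and SHBG group.

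Third, a specific restriction within a general rule need not be a contradiction, and overall might mean only all active against placebo. That would soften the conflict within 3.8.2.1. It would not reconcile the exclusion with the statement that the Safety Population serves all safety analyses.

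Fourth, Protocol 5.3 keeps those evaluating data blinded until database lock, and SAP 1 requires deviations to be documented. Neither fixes the excluded set. With an open list, almost no choice would count as a deviation.

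Finally, the sizes are illustrative. The above-target fraction is defined on total exposure, whereas the dose switch uses a 4-hour level of 1,500 ng/mL. The documents do not equate the two, and they give no size for the high-exposure or SHBG groups. That is correct.

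**Conclusion.** The concern holds. As written, the rule conflicts with the population named in the same paragraph and in SAP 3.2.3, SAP 3.8 and Protocol 10.1. It also permits an outcome value to decide who is analysed, with no closed list and no lock before unblinding.

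The size of any bias cannot be derived, because the documents give no rate of on-drug GGT or direct bilirubin triggers. One excluded patient moves a proportion by 1.4 points in the active arm, 2.9 in placebo and 4.8 to 5.6 in a 60 mg group of the assumed size. If only pre-dose values count, the effect is near zero.

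The exposure is confined to the dedicated liver enzyme analysis, provided the exclusion does not extend to the other laboratory tables; its wording leaves that scope unclear. This should be corrected before unblinding. It does not threaten the safety report as a whole.

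**What to change.** Make the full Safety Population the main analysis. Suggested text:

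> ALT, AST, CK and GGT will be analysed in the full Safety Population by treatment, exposure, final dose and SHBG group. Post-dose values do not exclude a patient.

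If an exclusion is wanted, keep it as a labelled sensitivity analysis with:
- a closed list of conditions;
- screening and Day 1 values only;
- a stated alcohol threshold, for example by reference to Protocol 4.2 (few patients would then qualify on alcohol, since that definition already bars entry);
- the excluded set fixed before unblinding;
- excluded patients listed by arm and reason.

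The SAP should also say that the exclusion does not apply to the by-visit, out-of-range and shift tables.

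The cost is SAP wording, the extra tabulation for the sensitivity version, and a listing of exclusions. No new data are needed.
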